4.1.2 Enrollment visit

The enrollment visit will be Day 1 of the study, which will correspond to the first day of study drug. During the enrollment visit, clinical history, examination findings and available laboratory results or radiology will be reviewed to ensure inclusion criteria are met and no exclusion criteria are present. The enrollment CRF will be completed. If participants meet entry criteria, they will be invited to participate in the clinical trial. After informed consent has been obtained, the participant will be allocated a study participant number and randomized to treatment allocation.

4.1.3 Informed consent

TBM is a medical emergency requiring prompt treatment so it is not necessary to wait for complete screening LP results before initiating TBM treatment and enrolling into the trial. The proximity to the screening visit will depend on the time required to make a provisional diagnosis of TBM. In most cases, there will be clear supporting evidence of TBM by clinical and/or CSF findings, whereas in other cases further investigation (e.g. to find evidence of extra-meningeal TB or perform brain imaging) may be required. Participants will not have their emergent diagnostic or medical care delayed.

All informed consent forms will be read in full to potential study participants. The consent forms will describe the purpose of the study, the procedures to be followed, and the risks and benefits of participation. The potential participant or their surrogate must be given sufficient time to review and ask questions. After sufficient time for consideration, study participants will sign all applicable consent forms prior to performance of any study-related procedures or administration of study-related medications. Study personnel obtaining consent must also sign the consent form. A copy of the consent form will be given to the participant or surrogate but if she/he does not want to keep a copy, it will be kept at the study site on behalf of the participant.

4.1.4 Assessment of capacity to provide informed consent

Potential participants will be evaluated by study personnel (medical officer or nurse) to determine if they have the capacity to provide consent. The Glasgow Coma Scale (GCS) will be used to assess level of consciousness and neurological status. Only participants with a GCS of 15 will be able to provide consent. In addition to having a GCS of 15, participants must also demonstrate understanding of the purpose and risks and benefits of the study and participate in a detailed review of the consent form with a trained study team member. If the study team member deems the participant's comprehension of the study to be appropriate, the participant will be able to provide consent. Otherwise, surrogate consent from the participant's next of kin/caregiver will be sought.

4.1.5 Surrogate Consent by a Next of Kin/Caregiver

A potential participant who lacks the capacity to provide informed consent due to altered mental status (e.g., confusion, somnolence, unconsciousness), which may be present in more than 50% of TBM patients, may be considered if they have a designated surrogate caregiver/next of kin who can consent on their behalf. The designated surrogate is a next of kin or caregiver who has the ability to provide consent for the participant's participation in this research protocol.

If participants regain the capacity to give consent, information will be provided to them and written informed consent will be sought for continuation in the trial. If a participant declines to give consent for continuation in the trial, they will be withdrawn. For participants enrolled by surrogate consent, capacity will be assessed regularly prior to hospital discharge and at clinic follow up visits.

4.1.6 Illiterate/Unable to Provide Signature

A participant who speaks and understands the language of the informed consent document, but does not read and write, can be enrolled in the study by "making their mark" or via a thumbprint on the informed consent document. In this event, an impartial, literate third party, which excludes study team members, must witness the entire consent process and sign the informed consent document. The witness's name, signature, and relationship must be recorded on the informed consent document.

4.1.7 Randomization

At study entry and prior to the 4th dose of TB treatment, participants will first be randomized by a computer-generated permutated block randomization (block size of 2 or 4) with a 1:1 randomization to high (35 mg/kg) versus standard dose (10 mg/kg) rifampicin. A second 1:1 randomization will then be performed to linezolid 1200 mg daily or no linezolid. Randomization will be stratified by British Medical Research Council (BMRC) TBM disease grade (Table 2), determined at the time of consent, given the association between worse disease severity and higher mortality¹.

Table 2. British Medical Research Council (BMRC) TBM disease grade

GRADE I	Glasgow coma score 15, no focal neurological signs
GRADE II	Glasgow coma score 11–14 with or without focal neurological sign or Glasgow coma score 15 with focal neurological signs
GRADE III	Glasgow coma score \leq 10 with or without focal neurological signs

The randomization schedules will be provided to the site pharmacy in a listed sequence. The sequential, unique randomization code will be recorded on the study entry CRF to assure there is no

skipping of the randomization order. All randomized participants will initiate their allocated study TB treatment within 24 hours of randomization and ideally the same day. For participants from whom informed consent has been obtained, but who are deemed ineligible or who do not enroll into the protocol, a Screening Failure form must be completed and entered into the database.

4.1.8 Co-enrollment Guidelines

Participants may be co-enrolled in observational studies but not in other interventional trials.

5.0 STUDY TREATMENT

Participants will be randomized in a factorial design to receive one of the following regimens shown in Table 3.

Arm	Weeks 1-4	Weeks 5-8*	Weeks 9-24*
А	R ₃₅ HZEL		
В	R ₁₀ HZEL	DUTE	D.U
С	R ₃₅ HZE		
D	R ₁₀ HZE		

Table 3: Study treatment regimens

Abbreviations: R, RIF; H, INH; Z, PZA; E, EMB; L, LZD;

*After the first 4 weeks of therapy, participants will receive treatment for TBM as per national guidelines.

Corticosteroid dosing: All participants will receive adjunctive corticosteroids, in addition to pyridoxine 50 mg daily.

Week 1: Dexamethasone IV 0.4 mg/kg/day

- Week 2: Dexamethasone IV 0.3 mg/kg/day
- Week 3: Prednisone PO 60 mg/day
- Week 4: Prednisone PO 50 mg/day
- Week 5: Prednisone PO 40 mg/day
- Week 6: Prednisone PO 30 mg/day
- Week 7: Prednisone PO 20 mg/day
- Week 8: Prednisone PO 10 mg/day

5.1 Administration

The intervention period will be for the first 4 weeks of TB therapy, after which all participants will receive the same standard therapy for TBM as per national guidelines.

Table 4: Treatment administration by weight bands through study period

		Interventi	ion period		Standard intensive phase Standard continuation phase									
					Week									
	1	2	3	4	5 to 8	10	12	16	20	24				

	Standard co-formulated TB treatment with addition rifampicin tablets	al 300mg	Standard in	tensive phase in all					
Arm	Weight Number of Additional RHZE tabs R 300mg (150/75/400/275 mg) tablets	Total R dose (mg)	participants guidelines	s, as per national	Standard continuation phase in all participants, as per national guidelines				
A	30-37 kg 2 tabs 3 tabs 38-54 kg 3 tabs 4 tabs 55-70 kg 4 tabs 5 tabs ≥ 71 kg 5 tabs 6 tabs	1200 1650 2100 2550	Weight 30-37 kg 38-54 kg 55-70 kg ≥ 71 kg	Number of RHZE tabs: (150/75/400/275 mg) 2 tabs 3 tabs 4 tabs 5 tabs	Weight 30-37 kg 38-54 kg 55-70 kg ≥ 71 kg	RH tabs (150/75mg) 2 tabs 3 tabs	RH tabs (300/150mg) 2 tabs 2 tabs		
	Standard co-formulated TB treatment								
Arm B	Weight Number of RHZE tablets: (150 / 75 / 400 / 275 mg) 30-37 kg 2 tabs 38-54 kg 3 tabs 55-70 kg 4 tabs ≥ 71 kg 5 tabs PLUS Linezolid (600 mg) 2 tablets								
	Standard co-formulated TB treatment with addition rifampicin tablets Weight Number of Additional	al 300mg							
Arm C	RHZE tabs R 300mg (150/75/400/275 mg) tablets 30-37 kg 2 tabs 3 tabs 38-54 kg 3 tabs 4 tabs 55-70 kg 4 tabs 5 tabs ≥ 71 kg 5 tabs 6 tabs	1200 1200 1650 2100 2550							
	Standard co-formulated TB treatment								
Arm D	Weight Number of RH2E tablets: (150 / 75 / 400 / 275 mg) 30-37 kg 2 tabs 38-54 kg 3 tabs 55-70 kg 4 tabs ≥ 71 kg 5 tabs								

The study pharmacist will dispense medication according to study arm and weight and will log all medication dispensed, the date, participant identification number and participant initials.

Intervention period: Weeks 1-4

Arm A: Fixed-dose combination tablets according to weight bands (Table 4) will be dispensed with additional 300 mg oral RIF tablets to equal a RIF dose of ~35mg/kg/day, along with standard dose INH ~5 mg/kg, PZA ~25 mg/kg, and EMB ~20 mg/kg. LZD 1200 mg daily will be dispensed as two 600 mg tablets. Participants will receive intact tablets or via nasogastric tube. If participants are discharged before the 4-week intervention period, they will be discharged with an adequate supply of study drug to last until the week 4 visit. Participants will be weighed at each visit and TB drug dose will be adjusted as necessary. Fixed dose combination antituberculous therapy will be prescribed through routine care pathways initially via the hospital and subsequently via linked TB clinics according to national guidelines.

Arm B: Fixed-dose combination tablets according to weight bands (Table 4) will be dispensed

to equal standard dosing for TBM treatment: oral RIF ~10 mg/kg, INH ~5 mg/kg, PZA ~25 mg/kg, EMB ~20 mg/kg. LZD 1200 mg daily will be dispensed as two 600 mg tablets.

Participants will receive intact tablets or via nasogastric tube. If participants are discharged before the 4-week intervention period, they will be discharged with an adequate supply of study drug to last until the week 4 visit. Participants will be weighed at each visit and TB drug dose will be adjusted as necessary. Fixed dose combination antituberculous therapy will be prescribed through routine care pathways initially via the hospital and subsequently via at TB clinics according to national guidelines.

Arm C: Fixed-dose combination tablets according to weight bands (Table 4) will be dispensed with additional 300 mg oral RIF tablets to equal a RIF dose of ~35mg/kg/day, along with standard dose INH ~5 mg/kg, PZA ~25 mg/kg, and EMB ~20 mg/kg. Participants will receive intact tablets or via nasogastric tube. If participants are discharged before the 4-week intervention period, they will be discharged with an adequate supply of study drug to last until the week 4 visit. Participants will be weighed at each visit and TB drug dose will be adjusted as necessary. Fixed dose combination antituberculous therapy will be prescribed through routine care pathways initially via the hospital and subsequently via linked TB clinics according to national guidelines.

Arm D: Fixed-dose combination tablets according to weight bands (Table 4) will be dispensed to equal standard dosing for TBM treatment: oral RIF ~10 mg/kg, INH ~5 mg/kg, PZA ~25 mg/kg, EMB ~20 mg/kg. Participants will receive intact tablets or via nasogastric tube. If participants are discharged before the 4-week intervention period, they will be discharged with an adequate supply of study drug to last until the week 4 visit. Participants will be weighed at each visit and TB drug dose will be adjusted as necessary. Fixed dose combination antituberculous therapy will be prescribed through routine care pathways initially via the hospital and subsequently via TB clinics according to national guidelines.

Standard intensive phase: Weeks 5-8

For the remainder of the standard intensive phase of treatment, all participants in all arms will receive standard treatment as per Ugandan national guidelines (**Table 4**), which recommend a total of 8 weeks of 4-drug therapy with RIF, INH, PZA, and EMB. Where isoniazid monoresistance or another clinical indication exists for alternative regimen this should be discussed with the treating clinician and PI.

Standard continuation phase: Weeks 9-24

For the continuation phase of treatment during the study period, all participants in all arms will receive standard treatment as per Ugandan national guidelines (**Table 4**), which recommend an additional 10 months of RIF and INH. After the study period ends at 24 weeks, participants will continue to receive routine care through TB clinic. Where isoniazid monoresistance or another clinical indications exist for alternative regimen this should be discussed with the treating clinician and PI.

5.2 Acquisition

The study will provide all TB medications for the first 4 weeks that are **not** part of current standard of care. This includes single drug formulation of rifampicin 300 mg tablets (Brand Name Rifacos, Cosmos Ltd), along with linezolid 600 mg tablets (Brand Name Lizolid, Star Pharmaceuticals Ltd), both of which will be purchased locally. Fixed-dose combination tablets will be supplied by the clinical site as part of routine care from a licensed nationally approved source.

5.3. Product Storage and Stability

The study medication will be stored at the site's secure pharmacy. All drugs will be protected from light and stored at room temperature (at or below 25^oC in adherence with manufacturers' instructions and documented on a temperature log in the pharmacy). If study medication has expired, it will be destroyed according to the local regulations. At the conclusion of the trial study medication will be

destroyed.

5.4 Study Product Accountability

The site pharmacist is required to maintain complete records of all dispensed study medications. Clinical personnel involved in the dispensation and administration of study drugs will adhere to Good Clinical Practice guidelines. Compliance with the protocol will be assessed via on-going quality assurance monitoring. A record of study medication final accountability and destruction will be kept and filed throughout.

5.5 Concomitant Medications

All concomitant prescription medications will be recorded on medication CRFs. Concomitant medications that are prohibited for the duration of the study due to known interactions with rifampicin include protease inhibitors (ritonavir, atazanavir, lopinavir), as rifampicin substantially reduces concentrations, which may result in loss of antiviral efficacy and development of HIV resistance. Due to a substantial reduction in the concentration of atovaquone, clarithromycin, digoxin, posaconazole, quinine, and voriconazole, rifampicin should also not be used concurrently with any of these drugs. There is not a danger in taking these medications; however, clinical investigators are advised to use alternatives for these medications. Monoamine oxidase inhibitors and selective serotonin reuptake inhibitors are also prohibited due to interactions with linezolid, in addition to tricyclic and other anti-depressant, lithium, carbamazepine, diphenhydramine, atypical antipsychotics, and anti-Parkinsonian medications (see **Appendices C and D**). Patients using systemic hormonal contraceptives should change to a non-hormonal method during rifampicin therapy. Barrier contraception is required for sexually active women of childbearing potential.

5.6 Adjunctive Corticosteroids

Adjunctive corticosteroid treatment has been shown to improve survival in TBM and is recommended for all patients with CNS TB according to WHO guidelines. Persons in *Strongyloides stercoralis* endemic regions are recommended to receive albendazole 400 mg orally twice daily for three days to reduce the risk of Strongyloides hyperinfection.

5.7 Antiretroviral Therapy

In a randomized trial of TBM participants in Vietnam, immediate ART did not improve survival and was associated with significantly more grade 4 adverse events compared with delayed ART initiation at 8 weeks.⁴⁶ As there is no available evidence that earlier ART confers a survival advantage, the international standard for ART initiation in persons living with HIV with TBM is currently at about 8 weeks.⁴⁶ HIV-infected participants not already receiving ART will be recommended to initiate ART at about 8 weeks after TB treatment initiation according to international guidelines. For persons on ART presenting with virologic failure, they would switch regimens at about 8 weeks after initiation of TB treatment. Appropriate counselling will be undertaken in HIV clinics. ART regimens will be prescribed and provided per National HIV Treatment Guidelines. HIV-infected participants will receive cotrimoxazole prophylaxis, unless allergic. We expect that the majority of our HIV-infected participants will not be receiving ART at TBM presentation; according to WHO guidelines they will be offered ART 8 weeks after starting TB treatment. Earlier initiation of ART is associated with an increase in adverse events and does not reduce mortality.³⁶ Early ART is associated with immune reconstitution inflammatory syndrome (IRIS), which can be fatal in TBM. Patients who are culture positive for *M. tuberculosis* from CSF at TBM diagnosis are also at increased risk of TBM-IRIS.³⁷

6.0 CLINICAL AND LABORATORY EVALUATIONS

6.1 Schedule of evaluations (Table 5)

Table 5: Schedul	Table 5: Schedule of evaluations												
Evaluation		Entry	Day	Wk	Wk	Wk	Wk	Wk	Wk	Wk	Wk 24	Sick	Early
	Screen ^a	(Day 1)	2	1	2	3	4	8	12	18		visit, Rx	with-
												relapse	ulawai
Visit window (days)			+/- 1	+/-1	+/-2	+/-2	+/-2	+/-	+/-	+/-14	+/-14		
								7	7				
Complete medical history	•												
Symptom assessment		•	•	٠	•	•	•	•	•	•	•	•	•
Medication review	•	•	•	•	•	•	•	•	•	•	•	•	•
Adherence assessment				•	•	•	•	•	•	•	•	•	•
Complete physical exam	•												
Targeted exam		•	•	•	•	•	•	•	•	•	•	•	•
Neurologic exam with	•	•	•	•	•	•	•	•	•	•	•	•	•
Glasgow Coma Scale													
MRC TBM disease grade	•	•	•	•	•	•	•	•	•	•	•	•	•
Brief peripheral	•			•	•		•	•					•
neuropathy screen													
Vision testing	•			٠	•		•	•					•
Neurocognitive testing									•		•		•
Patient Health									•		•		•
Questionnaire-9													
Modified Rankin Scale							•		•		•		•
Hematology ^b	•	•		•	•		•					 if indicated 	 if indicated
Chemistries ^b	•	•		•	•		•					• if	• if
Liver function testebs	•	•		•	•		•					indicated	
Liver function tests	_	-					_					indicated	indicated
Pregnancy test	•						As clinic	ally ind	icated				
Documentation of HIV	•												
CD4 count		•										• if	• if
												indicated	indicated
Lumbar puncture for CSF	•		•		•		 op- tional if 					• if indicated	• if
cell count, glucose,							out-					mulcated	indicated
protein, AFB smear and							patient						
	-						• 11 0						
	•						 If LP done 						
Chest x-ray ^d	•												
Head CT scan	 if indicated 											 if indicated 	 if indicated
Plasma PK ^e			•		•		•						
CSF PK ^e			•		•		•						
Stored TB isolate	•												
Stored plasma	•	•	•		•		•					•	•
Stored CSF	•		•		•		•					•	•

^aScreening evaluations can occur as part of routine care

^bCan defer at entry if screening labs obtained within 72 hours prior to entry

^cInclude hepatitis B surface antigen, hepatitis C antibody, and INR if ALT abnormal.

^dCan use chest x-ray and lumbar puncture performed as part of routine clinical care **within 14 days prior to screening.** Repeat lumbar puncture must be performed if AFB smear, culture, or Xpert Ultra were not performed prior to screening.

eIntensive PK sampling at Day 2, sparse sampling at Week 2; CSF PK at Week 4 if LP performed

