Cumulative toxicity is less of a concern when adjunctive LZD is administered for a short duration.³²⁻³⁴ LZD's narrow therapeutic window has tempered the enthusiasm for its therapeutic utility for TB. While most treatment-limiting toxicities, including myelosuppression, gastrointestinal (GI) symptoms and optic neuropathy, are reversible, some, including a painful, sensory-predominant neuropathy, may be permanent.^{35,36} LZD toxicity is driven by both dose and duration.³⁷ In 796 patients with gram-positive bacterial infections on LZD 600 mg BID, hematologic toxicities correlated with treatment duration, occurring in 5% of patients on LZD for 2 to 4 weeks. Peripheral neuropathy occurred in only 3 individuals with a mean treatment duration of 95 days.³⁸ Among 85 patients with DR TB on LZD, the majority of AEs occurred after 2 months.³³ Of 33 patients on LZD 1200 mg for XDR TB, anemia and GI symptoms were common (~50%) but necessitated discontinuation in only 2 patients within the first month.³⁹ No cases of peripheral or optic neuropathy occurred before 2 months. We will use a short course of adjunctive LZD, which has not been studied in a randomized trial for TBM, early in intensive therapy to augment bactericidal activity during the logarithmic growth phase of TB while minimizing cumulative toxicity.

Linezolid and the CSF compartment

CSF to plasma concentration ratios of 0.6 to >0.9 support good to excellent CNS penetration of LZD. However, the distribution of LZD in the CSF, from small studies of mostly neurosurgical patients, varies substantially. After a one-time dose of LZD 600 mg IV, mean CSF maximum concentrations (C_{max}) ranged from 5.1 to 6.6 ug/mL. At steady state, CSF C_{max} was 1.3 to 7.1 and up to 10.8 µg/mL, and minimum concentrations (C_{min}) were <0.2 to 3.1 and up to 6.1 µg/mL. The ability to achieve adequate CSF concentrations for sufficient duration has been inconsistent. One study found CSF LZD concentrations were >4 µg/mL for the entire dosing interval, while in another few patients reached concentrations >1 µg/mL. The minimum inhibitory concentration for 90% of isolates (MIC₉₀) is generally <0.5 µg/mL.

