6.3.4 Assessment of adherence

Participants will be hospitalized for the first 2 weeks of therapy, during which directly observed therapy will occur. After 2 weeks, participants can be discharged at the discretion of the inpatient physician. Once discharged, adherence will be assessed at in-person follow up visits by self-report (or by proxy report) and pill counts. Study staff will also endeavor to contact participants weekly by phone for remotely observed therapy.

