8.1.2 Hematological toxicity

A hematological toxicity management plan will be implemented if any of the following criteria are met:

- Hemoglobin < 7.0 g/dL for men, <6.5 g/dL for women
- Platelets <50,000/mm³
- Absolute neutrophil count <600/mm³

Management plan:

1. Discontinue linezolid

- 2. Assess for use of other myelosuppressive medications and discontinue non-essential medications (e.g., co-trimoxazole)
- Repeat blood count will be performed every 2 (+/-1) days until stable. If the abnormal hematological parameter(s) returns to Grade <2 and any associated symptoms resolve, linezolid 1200 mg can be restarted.
- 4. Continue to follow blood count every 2 (+/-1) days until stable. If after restarting linezolid, the abnormal hematological parameter returns to the above criteria, linezolid should again be discontinued.
- 5. Continue to follow blood count every 2 (+/-1) days until stable. If the abnormal hematololgical parameter(s) returns to Grade <2 and any associated symptoms resolve, linezolid can be restarted at 600 mg daily.
- 6. Continue to follow blood count every 2 (+/-1) days until stable. If after restarting linezolid, the abnormal hematological parameter returns to the above criteria, linezolid should be discontinued permanently.

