10.2 Planned analyses

The primary outcomes will be CSF and plasma LZD PK parameters, including CSF to plasma ratio, rate of CSF uptake, and plasma absorption rate constant (k_a), drug clearance (Cl/F), volume of distribution (V_d). We will employ a model-based approach using non-linear mixed effects modeling in NONMEM to estimate plasma and CSF PK parameters based on simultaneous analysis of all plasma and CSF drug concentration data.⁷⁴ We will perform post-hoc Bayesian predictions of secondary LZD PK parameters, including C_{max} , time to C_{max} , AUC₀₋₂₄, and elimination half-life in plasma and in CSF. Based on this approach, we will characterize the dynamic uptake of LZD in the CSF when administered with high and standard dose RIF over 4 weeks and derive a dosing algorithm for LZD to achieve target exposures through simulations. Pharmacodynamic breakpoints for LZD against TB are not established, but we will use target AUC₀₋₂₄, AUC/MIC, T>MIC for LZD of 160 µg*hr/mL, 100, and 85%, respectively.^{23,75,76} We will use sparse sampling to estimate the AUC curve based on CSF sampling early, at steady state, and before LZD discontinuation.⁷⁷

For the LZD adverse event evaluation, the primary outcome will be a dichotomous measure of Grade 3 or higher (yes/no) myelosuppression (e.g., anemia, thrombocytopenia, leukopenia) during the 4 weeks of therapy. A secondary outcome will be LZD discontinuation or dose reduction (yes/no) for any AE. We will compare the frequency of myelosuppression between the LZD and no LZD arms across RIF dosing with the Cochran-Mantel-Haenszel test, which accounts for stratified randomization. Within

the LZD arm, we will explore differences in the frequency of myelosuppression between the standard and two high dose RIF arms combined by a chi-square test. We will use an exposure-response model using logistic regression to test if the probability of myelosuppression and LZD discontinuation is related to PK measurements, including C_{min} , C_{max} and AUC₀₋₂₄.

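### Table 5 schedules no blood count between Week 2 and Week 4, so for the powered myelosuppression outcome the second half of linezolid dosing is not checked until about its end

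*Combined protocol and SAP*

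**What the plan says.** - **Schedule.** In the table under "6.1 Schedule of evaluations (Table 5") the hematology row is marked at screening, entry and Weeks 1, 2 and 4. At sick visits and early withdrawal a count is taken only if indicated. Week 3 has symptom, medication and adherence review and targeted and neurologic examinations, but no blood draw. Its window, like those of Weeks 2 and 4, is +/-2 days.
- **Dosing.** Section 5.1: "The intervention period will be for the first 4 weeks of TB therapy".
- **Safety rule.** Section 8.1.2 is entered on hemoglobin, platelet or neutrophil thresholds. Once entered, counts repeat every 2 (+/-1) days until stable, and linezolid is stopped and restarted in steps, including "linezolid can be restarted at 600 mg daily".
- **Outcome.** Section 10.2 makes the main adverse event outcome "Grade 3 or higher (yes/no) myelosuppression (e.g., anemia, thrombocytopenia, leukopenia) during the 4 weeks of therapy". Section 10.1 assumes 40% on linezolid against 10% without, and states at least 80% power with 30 per arm.
- **Setting.** Section 6.3.4: "After 2 weeks, participants can be discharged at the discretion of the inpatient physician". Section 7.4 expects about 40% mortality, and Section 1.0 puts most deaths in the first month.

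**The concern.** Counts become sparser as cumulative linezolid exposure grows, and they do so when participants may leave hospital. Two things depend on those counts.

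First, 8.1.2 needs a laboratory value. A participant without symptoms whose count crosses a threshold after Week 2 has no scheduled trigger until dosing is nearly or fully over.

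Second, the four-week outcome rests on three scheduled post-entry counts (Weeks 1, 2 and 4). A participant who dies or withdraws between Weeks 2 and 4 may have no count after Week 2. Other counts in that interval depend mostly on clinical judgement. The trial is open label, and Section 4.0 commits only to trying to blind the staff who assess adverse events. If unscheduled counts are ordered more readily in known linezolid recipients, the two arms are not measured alike.

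**Working it through.** **1. The gap.** Section 6.3.18 equates Week 4 with Day 28 and places the second sampling at Day 14, so Week 3 is Day 21. With the +/-2-day windows:

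| Interval between scheduled counts | Shortest | Nominal | Longest |
|---|---|---|---|
| Week 2 to Week 4, as written | (28-2)-(14+2) = 10 days | 28-14 = 14 days | (28+2)-(14-2) = 18 days |
| With a Week 3 count: Week 2 to 3 | (21-2)-(14+2) = 3 days | 7 days | (21+2)-(14-2) = 11 days |
| With a Week 3 count: Week 3 to 4 | (28-2)-(21+2) = 3 days | 7 days | (28+2)-(21-2) = 11 days |

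**2. Delay to detection.** Assume that asymptomatic threshold crossings are spread evenly over Days 14 to 28 and persist until the next count. The mean delay is half the interval: 14/2 = 7 days as written, and 7/2 = 3.5 days with a Week 3 count. The documents give no onset distribution, so this is an illustration.

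**3. The stated power.** Inputs from Section 10.1: 40% against 10%, 30 per arm, significance level 0.05 (taken as two-sided; the protocol does not say).

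- Unpooled normal approximation: 0.30 / sqrt(0.24/30 + 0.09/30) = 2.86; 2.86 - 1.96 = 0.90; power about 81.6%.
- Exact enumeration of the uncorrected chi-square test: 79.6%.
- Pooled-variance formula: 78.0%.

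The stated figure of at least 80% is reproduced within the spread of ordinary methods, with essentially no margin.

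**4. Sensitivity to missed events.** The documents do not give the share of events that the gap would lose. If the same share is lost in both arms, both rates shrink by that share. On the pooled formula:

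| Share missed (assumed) | Rates compared | Power |
|---|---|---|
| 0% | 40% v 10% | 78.0% |
| 10% | 36% v 9% | 71.7% |
| 20% | 32% v 8% | 64.9% |
| 30% | 28% v 7% | 57.5% |

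These rows show how little slack there is. They do not predict the loss.

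**5. What else could supply a count between Weeks 2 and 4.**

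- Extra tests at the physician's discretion with the site PI's agreement (6.3.13), closer follow-up after a Grade 2 toxicity (8.1.6), and sick-visit tests (6.2.4). All depend on a judgement or on a prior finding.
- Platelets within 72 hours before a lumbar puncture (6.3.14). The Week 4 puncture may fall on Day 26, so this check could come as early as Day 23. It requires platelets only, and that puncture may be optional for participants no longer in hospital.
- Repeat counts under 8.1.2, which need an earlier triggering count.

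None is a scheduled full count that applies alike to all four arms.

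**The case against.** The strongest reply is that the existing schedule works for most events. Weeks 1 and 2 are on-treatment counts that can start 8.1.2. A cytopenia that persists to Week 4 is found then and counts in the yes/no outcome. The Week 4 count may fall on Day 26, with doses left. Inpatients are reviewed daily, and discharge after Week 2 is optional. Nothing in the documents suggests that a cytopenia would recover while linezolid continues, so the clearest routes to a missed event are death and withdrawal. All of this stands, and it limits the size of the point.

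A reader might also infer more than the documents support:

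- *That the protocol places linezolid cytopenias in Weeks 2 to 4.* Section 1.0 says "hematologic toxicities correlated with treatment duration, occurring in 5% of patients on LZD for 2 to 4 weeks". That is a rate by length of treatment, not an onset window. The same section reports that in 33 patients on 1200 mg "anemia and GI symptoms were common (~50%) but necessitated discontinuation in only 2 patients within the first month", and that in another series "the majority of AEs occurred after 2 months". At 5%, 30 linezolid participants would yield 0.05 x 30 = 1.5 events; at the planning rate of 40%, 12.
- *That cytopenias go unseen and 8.1.2 cannot act.* Any count can trigger the rule, scheduled or not. What is missing is scheduled detection.
- *That a count is also needed at Week 8.* Planned linezolid ends at Week 4 and so does the outcome window, so a later count adds nothing to on-treatment safety or to this outcome.
- *That a number of lost participants can be stated.* About 0.40 x 30 = 12 deaths are expected among those on linezolid, but the documents do not say how many fall between Weeks 2 and 4.

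**Conclusion.** The point holds as a modest gap in ascertainment. No count is scheduled between Week 2 and Week 4 (14 days nominally, 10 to 18 with windows), although a visit already falls in the middle. Asymptomatic cytopenias arising in that interval are detected on schedule only at about the end of dosing, and may be missed in participants who die or withdraw before then. Partial cover from discretionary tests may differ by arm because allocation is known.

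The gap length follows directly from Table 5. The 7-day mean delay assumes evenly spread, persistent events, and the power figures assume a missed share that the documents do not supply. Table 5 does not contradict 8.1.2 or 10.2 outright, since both can operate on the existing counts. It serves them less well in the second fortnight than in the first.

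**What to change.** In the hematology row of Table 5, add a mark at the existing Week 3 visit for all four arms, on the same terms as Weeks 1, 2 and 4. The outcome is then measured weekly and identically across arms, in line with 8.1.2 and the four-week window in 10.2. Section 6.3.13 already requires every post-entry laboratory value on the CRF, so the result enters the outcome without a new form. No dose, threshold or stopping rule changes.

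The cost is one extra routine venous draw per participant: at most 60 counts for the planned 60 participants, fewer after deaths, at a visit already in the schedule. If the sponsor keeps the present schedule, the protocol should say why, and Section 10.2 should state how participants with no count after Week 2 are classified in the outcome.
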